6.4. Study Vaccination Compliance

Study vaccines will be administered IM by a unblinded qualified study vaccine administrator a trained and qualified study nurse, medical doctor, or otherwise qualified HCP at the study site. For blinding procedures, see Section 6.3. The date and time of study vaccine administration and the location of injection will be recorded in the eCRF.

6.5. Dose Modification

The safety, reactogenicity and available immunogenicity data of participants in the Dose Selection Cohort (2.5×10^{10} vp, 1.25×10^{10} vp, and 0.625×10^{10} vp dose levels) will be reviewed by the IDMC (see Section 4.1). The lowest dose level (and any/all lower dose levels) that is deemed to produce acceptable reactogenicity, provided it induces adequate immunogenicity, as identified during this review, will be considered for future development.

6.6. Treatment of Overdose

For this study, any dose of Ad26.COV2.S greater than the highest dose tested in the study will be considered an overdose. The sponsor does not recommend specific treatment for an overdose.

In the event of an overdose, the investigator should:

- Contact the medical monitor immediately.
- Closely monitor the participant for AEs/SAEs/MAAEs: the participant will remain at the study site for at least 1 hour and will be closely monitored for allergic or other reactions by site staff. Follow-up telephone calls 12 hours and 24 hours post-vaccination will be made.

- Document the quantity of the excess dose in the eCRF.
- Report as a special reporting situation.

6.7. Prestudy and Concomitant Therapy

Prestudy therapies such as analgesic/antipyretic medications and non-steroidal anti-inflammatory drugs, corticosteroids, antihistamines, and vaccinations administered up to 30 days before the first dose of study vaccine must be recorded at screening.

Concomitant therapies such as, but not limited to, analgesic/antipyretic medications and non-steroidal anti-inflammatory drugs, corticosteroids, antihistamines, and vaccinations must be recorded from the moment of first vaccination until 28 days after administration of study vaccine, and thereafter, pre-dose on the day of any subsequent vaccination and for 28 days after that vaccination. All other concomitant therapies should also be recorded if administered in conjunction with a confirmed COVID-19 case or with new or worsening AEs or suspected AESIs reported per protocol requirements outlined in Section 8.3.1. Concomitant therapies associated with an SAE meeting the criteria outlined in Section 10.4.1 will be collected and recorded in the eCRF from the moment of first vaccination through the end of the study. Concomitant therapies associated with MAAEs will be collected and recorded in the eCRF from the moment of vaccination until 6 months after vaccination. Concomitant therapies associated with MAAEs leading to study discontinuation will be recorded in the eCRF from the moment of first vaccination through the end of the study.

Use of any experimental medication (including experimental vaccines other than the study vaccine) will lead to discontinuation of administration of any subsequent study vaccination. Participants may not receive an investigational drug (including investigational drugs for prophylaxis of COVID-19) or use an invasive investigational medical device within 30 days, or receive investigational or other immunoglobulin or monoclonal antibodies within 3 months, or receive convalescent serum for COVID-19 treatment within 4 months, or receive an investigational vaccine (including investigational Adenoviral-vectored vaccines) within 6 months before the planned administration of the first dose of study vaccine. During the study, the use of investigational vaccines other than the study vaccine is not allowed, and the use of investigational drugs is only allowed if medically indicated. Treatment with investigational COVID-19 drugs after diagnosis of a COVID-19 case is allowed during the follow-up period and needs to be recorded in the COVID-19 episode description.

Licensed live attenuated vaccines should be given at least 28 days before or at least 28 days after a study vaccination (14 days before and after for rotavirus vaccine in adolescents) and must be recorded. Other licensed (not live) vaccines (eg, the DTaP [reduced Diphtheria toxoid, Tetanus toxoid, and acellular Pertussis], influenza, tetanus, hepatitis A, hepatitis B, rabies) should be given at least 14 days before or at least 14 days after a study vaccination in order to avoid potential confusion of adverse reactions and potential immune interference and must be recorded.

The use of any coronavirus vaccine (licensed or investigational) other than Ad26.COV2.S is disallowed at any time prior to vaccination and during the study. If a vaccine is indicated in a post-exposure setting (eg, rabies or tetanus), it must take priority over the study vaccine and should

be discussed with the sponsor to determine if continued study vaccination is feasible, and any vaccinations must be recorded. Adolescents receiving routine immunizations according to their local vaccination schedules (eg, in Europe, the applicable national immunization schedules, and the equivalent in other countries) should not be postponed due to study participation and all vaccinations must be recorded.

Antipyretics are recommended post-vaccination for symptom relief as needed. Prophylactic antipyretic use is not encouraged, however, in some instances, it could be considered for participants only in special circumstances.

Chronic (>14 days) or recurrent use of systemic corticosteroids^a, at immunosuppressive doses and administration of antineoplastic and immunomodulating agents or radiotherapy are prohibited during the study and within 6 months before the planned administration of the first dose of study vaccine. If any of these agents are indicated in a disease setting, these must take priority over the study vaccine.

Refer to Section 5.2, Exclusion Criteria for further details of prohibited therapy.

The sponsor must be promptly notified of any instances in which prohibited therapies are administered. The participant should remain in the study but receive no further study vaccination. Depending on the time of the occurrence, a participant who receives a prohibited concomitant medication will not be included in the immunogenicity analyses.

6.8. Study Vaccination Pausing Rules

The principal investigator (PI) and the study responsible physician/scientist (SRP/SRS) will monitor safety in a blinded manner, including the study vaccination pausing rules. If a study vaccination is considered to raise significant safety concerns (and a specific set of pausing criteria have been met), further vaccination of participants will be paused. The concerned data will be reviewed by the IDMC, after which the IDMC will recommend whether the pause can be lifted or not, or whether other steps are needed.

The IDMC will review blinded data first but has the right to request the randomization codes and review unblinded data if deemed necessary. The IDMC will make recommendations regarding the continuation of the study to the sponsor study team. The sponsor study team will communicate conclusions regarding study continuation to the investigator, the IEC / IRB, and applicable health authorities as appropriate.

After the first IDMC meeting triggered by the occurrence of a given pausing rule, the IDMC will convene thereafter for each additional participant meeting that pausing rule.

The occurrence of any of the following events will lead to a pause in further study vaccination (once the pause is lifted, the decision regarding subsequent vaccination [if applicable] will be

^a Note: Ocular, topical, or inhaled steroids are allowed. Non-immunomodulator treatment is allowed as well as steroids at a physiologic dose.

assessed on a case by-case basis, upon discussion between sponsor and investigator). Laboratory abnormalities noted below refer to cases where the study-site personnel perform laboratory safety testing for investigation of an AE.

1. Death of a participant, considered related to study vaccine or if the causal relationship to the study vaccine cannot be excluded; OR

Note: All cases of death will be sent to IDMC for information. Upon their review, IDMC may then decide whether a study pause is required.
2. One or more participants experience an SAE or a Grade 4 (solicited or unsolicited) AE or a persistent (upon repeat testing) Grade 4 laboratory abnormality that is determined to be related to study vaccine; OR
3. One or more participants experience anaphylaxis or generalized urticaria, clearly not attributable to other causes than vaccination with study vaccine; OR
4. One or more participants experience MIS-C which is assessed as at least possibly related to study vaccine; OR
5. Three participants from the Dose Selection Cohort (of the same dose level group, within the same age group, and from the same 2 dose vaccination regimen with 1 or 2 active vaccinations, with placebo administered as a second dose for those in the 1-dose regimen) experience a Grade 3 unsolicited AE of the same type (per medical judgement of the sponsor), that is determined to be related to study vaccine; OR
6. Three participants from the Dose Selection Cohort (of the same dose level group, within the same age group, and from the same 2 dose vaccination regimen (56-day interval) with 1 or 2 active vaccinations, with placebo administered as a second dose for those in the 1-dose regimen) experience a persistent (upon repeat testing) Grade 3 laboratory abnormality related to the same laboratory parameter and considered related to study vaccine; OR
7. Three participants from the Dose Selection Cohort (of the same dose level group, within the same age group, and from the same 2 dose vaccination regimen (56-day interval) with 1 or 2 active vaccinations, with placebo administered as a second dose for those in the 1-dose regimen) experience a Grade 3 solicited AE of the same type, determined to be related to study vaccine, and persisting as Grade 3 for longer than 3 consecutive days (ie, the day of occurrence of the AE is counted as Day 1).
8. One or more cases of suspected TTS, possibly related to the vaccine.

For number 2 and number 6: to assess abnormal laboratory values, the test must be repeated at least once, within 48 hours of the site becoming aware of the abnormal value.

For number 5, number 6, and number 7: after each IDMC review of similar AE, the committee will indicate the conditions under which it requires further notification and review of the subsequent similar AEs.

Note: the occurrence of a study pause in any other ongoing study with Ad26.COV2.S may trigger a study pause in further vaccination in the current study, if considered to be medically relevant. Any subsequent delayed study visits as a result of a delayed vaccination following a study pause are not considered to be protocol violations.

To enable prompt response to a situation that could trigger pausing rules, the investigator should notify the sponsor's medical monitor or designee (AND fax or email the SAE form to Global Medical Safety Operations, if applicable), immediately and no later than 24 hours after becoming aware of any related AE of Grade 3 or above AND update the eCRF with relevant information on the same day the AE information is collected. A thorough analysis of all Grade 3 (or above) cases will be carried out by the sponsor's medical monitor or designee, irrespective of whether the criteria for pausing the study are met. Based on the pausing criteria, the sponsor's medical monitor or designee then decides whether a study pause is warranted. All sites will be notified immediately in case of a confirmed study pause. The sponsor's medical monitor or designee is responsible for the immediate notification of IDMC members and coordination of an IDMC meeting in case of a study pause no later than 24 hours after becoming aware.

Vaccinations for an individual participant may be suspended for safety concerns other than those described in the pausing criteria, at the discretion of the investigator if he/she feels the participant's safety may be threatened. The sponsor's medical monitor or designee may initiate IDMC review for any single event or combination of multiple events which, in their professional opinion, could jeopardize the safety of the participants or the reliability of the data.

Vaccinations for the study may be suspended for safety concerns other than those described above, or before pausing rules are met, if, in the judgement of the IDMC, participant safety may be threatened.

Resumption of vaccinations will start only upon receipt of written recommendations by the IDMC. The clinical site(s) will be allowed to resume activities upon receipt of a written notification from the sponsor. These recommendations from the IDMC will be communicated to investigators, IRB/IEC and relevant health authorities, according to local standards and regulations.

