Solicited AEs, collected through a reactogenicity diary as part of the eCOA, will be recorded for each vaccination from the time of vaccination until 7 days post-vaccination.

All other unsolicited AEs and special reporting situations, whether serious or non-serious, will be reported for each vaccination from the time of vaccination until 28 days post-vaccination. Unsolicited AEs with the onset date outside the timeframe defined above (>28 days after previous study vaccination), which are ongoing on the day of the subsequent vaccination, should be recorded as such.

All SAEs and AEs leading to discontinuation from the study/vaccination (regardless of the causal relationship) are to be reported for all participants from the moment of first vaccination until completion of the participant's last study-related procedure, which may include contact for safety follow-up. The sponsor will evaluate any safety information that is spontaneously reported by an investigator beyond the time frame specified in the protocol.

MAAEs are defined as AEs with medically-attended visits including hospital, emergency department, urgent care clinic, or other visits to or from medical personnel for any reason. Routine study visits will not be considered medically-attended visits. New onset of chronic diseases will be collected as part of the MAAEs. MAAEs are to be reported for all participants from the first vaccination until 6 months after each vaccination, except for MAAEs leading to study discontinuation which are to be reported during the entire study.

To enable prompt response to a situation that could trigger pausing rules, the investigator should notify the sponsor's medical monitor or designee (AND fax or email the SAE form to Global Medical Safety Operations, if applicable), immediately and no later than 24 hours after becoming aware of any related AE of Grade 3 or above AND update the eCRF with relevant information on the same day the AE information is collected as described in Section [6.8](#).

All AEs will be followed until resolution or until clinically stable.

Adverse Events of Special Interest

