From the time of local approval of protocol Amendment 1 onwards, TTS (Section [8.3.6.1](#)) and MIS-C (Section [8.3.6.2](#)) are considered to be AESIs. Suspected AESIs (thrombotic events and thrombocytopenia [defined as platelet count below 150,000/ μ L] [[BC 2021](#)], and MIS-C) will be recorded from the moment of vaccination until the end of the study/early withdrawal. An AESI Adjudication Committee with appropriate expertise will be established to evaluate each suspected AESI and determine cases of TTS (Section [8.3.6](#)).

Serious Adverse Events

All SAEs, as well as PQC, occurring during the study must be reported to the appropriate sponsor contact person by study-site personnel within 24 hours of their knowledge of the event.

Serious adverse events, including those spontaneously reported to the investigator, must be reported using an SAE form. The sponsor will evaluate any safety information that is spontaneously reported by an investigator beyond the time frame specified in the protocol.

Information regarding SAEs will be transmitted to the sponsor using the Serious Adverse Event Form and Safety Report Form of the eCRF, which must be completed and reviewed by a physician

from the study site, and transmitted to the sponsor within 24 hours. The initial and follow-up reports of an SAE should be transmitted electronically or by facsimile (fax). Telephone reporting should be the exception and the reporter should be asked to complete the appropriate form(s) first.

Signs and symptoms of MIS-C will be monitored and reported as SAE in adolescents with (suspected) COVID-19 as confirmed by a positive molecular test result for SARS-CoV-2, and in adolescents whose parents/caregivers or close relatives/contacts have a prior (within 4-weeks) or current suspected or confirmed COVID-19. Further details on case definition and reporting of MIS-C in adolescents can be found in Section 10.8.

8.3.2. Method of Detecting Adverse Events, Medically-attended Adverse Events, Adverse Events of Special Interest, and Serious Adverse Events

Care will be taken not to introduce bias when detecting AEs, MAAEs, suspected AESIs, or SAEs. Open-ended and nonleading verbal questioning of the participant is the preferred method to inquire about AE occurrence.

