10.3.6. Safety Monitoring Committees Structure

Independent Data Monitoring Committee

An IDMC will be established to monitor safety data on an ongoing basis to ensure the continuing safety of the participants enrolled in this study. The IDMC consists of members that are not directly involved in the study conduct, data management, or statistical analysis, will be established and will monitor data to ensure the continuing safety of the participants enrolled in this study. The IDMC

will consist of at least 1 medical expert in the relevant therapeutic area of pediatrics and at least 1 external statistician independent of the sponsor and not involved in the final analysis of the study who will prepare the data and perform all IDMC safety analyses for review by the IDMC. Committee membership responsibilities, authorities, and procedures will be documented in its charter.

The IDMC will review data as indicated in Section 4.1. IDMC safety reviews will be based on descriptive safety tables and listings from all accumulated safety data at that point in time. After each review, the IDMC will make recommendations regarding the continuation of the study. When appropriate, the conclusions of the IDMC will be communicated to the investigators, the IRB/IEC, and the national regulatory authorities.

Molecularly confirmed COVID-19 cases will be reported to the IDMC on a regular basis.

The IDMC responsibilities, authorities, and procedures will be provided in its charter.

Ad hoc review may be performed further to the occurrence of any AE/SAE leading to a study pausing situation as outlined in Section 6.8, or at request of the sponsor's medical monitor or designee. The PI and sponsor's study responsible physician will inform the IDMC of any AE of concern.

If any pausing rule is met (refer to Section 6.8) and, if following appropriate safety review it is deemed appropriate to restart dosing, the sponsor must submit a request to restart dosing with pertinent data to competent authority as a request for a substantial amendment, as required by local regulations or authority request (eg, MHRA). If needed, this will be followed by a substantial amendment of the IB and/or protocol.

AESI Adjudication Committee

An AESI Adjudication Committee with appropriate expertise will be established to evaluate each suspected AESI and determine whether it is a case of TTS (see Section 8.3.6). A Charter will be developed to describe the roles and responsibilities of the Committee.

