10.3.9. Case Report Form Completion

Case report forms are prepared and provided by the sponsor for each participant in electronic format. All data relating to the study must be recorded in the eCRF. All eCRF entries, corrections, and alterations must be made by the investigator or authorized study-site personnel. The investigator must verify that all data entries in the eCRF are accurate and correct.

The study data will be transcribed by study-site personnel from the source documents onto an eCRF, if applicable. Study-specific data will be transmitted in a secure manner to the sponsor.

Worksheets may be used for the capture of some data to facilitate completion of the eCRF. Any such worksheets will become part of the participant's source documents. Data must be entered into the eCRF in English. The eCRF must be completed as soon as possible after a participant visit and the forms should be available for review at the next scheduled monitoring visit.

All participative measurements (eg, questionnaires) will be completed by the same individual who made the initial baseline determinations whenever possible.

If necessary, queries will be generated in the electronic data capture (eDC) tool. If corrections to an eCRF are needed after the initial entry into the eCRF, this can be done in either of the following ways:

- Investigator and study-site personnel can make corrections in the eDC tool at their own initiative or as a response to an auto query (generated by the eDC tool).
- Sponsor or sponsor delegate can generate a query for resolution by the investigator and study-site personnel.

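### The 24-hour notice that serves the pausing rules starts at Grade 3, so a non-serious Grade 1 or 2 generalized urticaria can meet pausing rule 3 with no deadline for telling the sponsor

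*Protocol*

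**What the plan says.** Protocol Section 6.8 lists eight events that pause further vaccination. Rule 3 reads: "One or more participants experience anaphylaxis or generalized urticaria, clearly not attributable to other causes than vaccination with study vaccine". It names no grade and no seriousness criterion, and one participant is enough.

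The same section then sets out how the sponsor is to hear of such events. The investigator must notify the medical monitor "immediately and no later than 24 hours after becoming aware of any related AE of Grade 3 or above", and must update the eCRF on the day the information is collected. The stated reason is to allow a prompt response where a pausing rule might be triggered. Section 8.3.1 (All Adverse Events) repeats the requirement with the same limit: "no later than 24 hours after becoming aware of any related AE of Grade 3 or above".

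On receiving the information, the "medical monitor or designee then decides whether a study pause is warranted". The monitor must also notify the IDMC within 24 hours in case of a study pause.

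Two other reporting routes carry a 24-hour limit:

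- SAEs "must be reported to the appropriate sponsor contact person by study-site personnel within 24 hours of their knowledge of the event" (Section 8.3.1, Serious Adverse Events).
- AESIs are reported within 24 hours irrespective of seriousness (Section 8.3.6), but the AESIs in this study are only TTS and MIS-C.

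**The concern.** The notification exists to serve the pausing rules, but its entry condition is narrower than one of the rules it serves. A site could hold a confirmed case of vaccine-caused generalized urticaria, which on its own requires a pause, and be under no timed obligation to tell the person who decides on that pause. The monitor's 24-hour duty towards the IDMC does not help, because it cannot start until someone has told the monitor.

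What is at stake is participant protection, not estimation. Section 2.1 starts both age groups and all dose levels at the same time, so other adolescents may still be vaccinated after a pausing criterion has been met and is known at one site.

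**Working it through.** No sample size, error rate or event count is involved, so there is no formula to apply. The check is to trace each pausing rule in Section 6.8 to a reporting route with a fixed limit.

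| Rule | Event | Route with a 24-hour limit | Every qualifying event covered? |
|---|---|---|---|
| 1 | Death, related or relation not excluded | SAE | Yes |
| 2 | Related SAE, Grade 4 AE or persistent Grade 4 laboratory abnormality | SAE, or related Grade 3+ notice | Yes |
| 3 | Anaphylaxis or generalized urticaria caused by vaccine | SAE or Grade 3+ notice, only if the case qualifies | **No** |
| 4 | MIS-C, at least possibly related | AESI | Yes |
| 5 | Three related Grade 3 unsolicited AEs of one type | Related Grade 3+ notice | Yes |
| 6 | Three related persistent Grade 3 laboratory abnormalities | Related Grade 3+ notice (Section 10.4.1 counts laboratory abnormalities as AEs) | Yes |
| 7 | Three related Grade 3 solicited AEs lasting more than 3 days | Related Grade 3+ notice | Yes |
| 8 | Suspected TTS, possibly related | AESI | Yes |

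Result: 7 of 8 rules are fully covered, and 1 of 8 (rule 3) is partly covered.

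The next question is whether generalized urticaria can be graded below 3.

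- Urticaria has no row of its own in the grading tables of Section 10.5. Under the general guideline in Section 10.4.3, Grade 3 needs two things together: inability to carry out usual activities, and a need for medical intervention. An adolescent with widespread hives who carries on with normal activities is Grade 1 or 2 on that scale, even if treated.
- If the generic illness row of Section 10.5 is used instead, Grade 2 is reserved for events that need no medical intervention, so a treated case is harder to place below Grade 3. But Grade 3 in that row also requires that daily activity is prevented. The row narrows the gap without closing it.
- An emergency-room visit or hospitalization makes the event Grade 4 under Section 10.4.3 and brings it inside the notice.

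The uncovered case is therefore generalized urticaria, clearly vaccine-caused, non-serious, Grade 1 or 2, with no emergency-room visit.

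Neighbouring text does not fill the gap:

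- The mandatory case analysis by the medical monitor in Section 6.8 also starts at Grade 3.
- Section 7.1 names anaphylactic reaction as a reason to withhold further doses but does not name generalized urticaria, so even the affected participant's next dose rests on the investigator's opinion.
- The PI and the study responsible physician "will monitor safety in a blinded manner, including the study vaccination pausing rules" (Section 6.8), with no time limit.
- The PI and the sponsor's "study responsible physician will inform the IDMC of any AE of concern" (Section 10.3.6), with no time limit.
- "The eCRF must be completed as soon as possible after a participant visit" (Section 10.3.9), with no fixed number of hours or days.

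**The case against.** The strongest reply is that the residual case hardly exists. The event must be generalized, clearly vaccine-caused (a stricter test than related), below Grade 3, without an emergency-room visit, and judged not medically important. Section 10.4.1 says that important medical events should usually be treated as serious, and an event listed beside anaphylaxis as a single-case reason to stop vaccination is a good candidate. Exclusion criteria 3 and 8 remove people with known or suspected vaccine allergy and with chronic urticaria, which should make a new case rarer and more conspicuous.

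The other duties are also mandatory. The PI who concludes that rule 3 is met is one of the people charged with monitoring the pausing rules, Section 10.3.6 says the IDMC will be informed, and staff observe each participant for at least 30 minutes after vaccination. Operational timing may be set in sponsor instructions, the eCRF completion guidelines or the IDMC Charter, none of which is in the file. Nothing here touches an endpoint or an analysis set.

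Most of this stands as a limit on size. The case is narrow, an attentive PI would probably telephone, and the finding concerns the protocol text only. It does not remove the gap. Classifying the event as medically important is a judgement, and the monitoring and IDMC duties set no time by which the medical monitor must know. The exclusions affect frequency, not what happens when a case occurs.

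**Conclusion.** The concern holds, as a minor point. Rule 3 is the only one of the eight pausing rules that can be met by an event outside every 24-hour route, and it needs just one participant. The limit is 24 hours for every event under the other seven rules; for the residual rule 3 case none is stated.

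The number of doses given in the interval cannot be estimated: the documents give neither the frequency of such urticaria nor the usual delay before non-expedited AEs reach the sponsor. The conclusion assumes that the investigator does not class the event as serious and that no document outside the protocol and SAP sets a time limit. It has no bearing on the immunogenicity or safety analyses.

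**What to change.** In Sections 6.8 and 8.3.1, extend the 24-hour notification and the same-day eCRF update to cover any related AE of Grade 3 or above, or any event that could meet a pausing rule, including generalized urticaria, regardless of grade or seriousness. The pausing rules themselves need no change.

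The cost is one clause in two sections and a memo to sites. The downside is a few additional expedited notices.
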